1. Infertile women planning to undergo IVF/ICSI cycle using conventional GnRH agonist long protocol or GnRH antagonist protocol
2. Age ≤ 38 years old
3. Basal AFC 8~20
4. Basal FSH ≤ 10 IU/L
5. Basal E₂ < 200 pmol/L

6. Normal uterus and at least one side of the normal ovary
7. Informed consent form signed
8. Willing to follow the study protocol, and able to complete this study

Exclusion criteria:

1. Previous IVF/ICSI cycles >2
2. Severe hydro-salpinx (Ultrasound shows hydro salpinx > 2cm)
3. Severe endometriosis (Grade III – IV)
4. Polycystic ovarian syndrome (PCOS)
5. History of recurrent miscarriages (>2 times of miscarriages)
6. Plan to undergo ovarian stimulation for preimplantation genetic diagnosis or preimplantation genetic screening, oocyte donation, and social or medical freezing of oocytes
7. Any major systemic disease that as per Investigator's discretion precludes subject for participation in the study
8. With pregnancy contraindications
9. Alcoholism, drug abuse, drug addiction or patients with uncured sexually transmitted disease
10. According to the judgment of the Investigator, any medical condition or any concomitant surgery/medications that would interfere with evaluation of study medications
11. Simultaneous participation in another clinical study
12. Plan to use urinary gonadotrophin during COS treatment

Investigational Medicinal Product:

GnRH-a group: The GnRH-a (Diphereline[®] or Decapetyl[®]) 0.1mg will be administered for about 14 to 20 days for down-regulation. Recombinant FSH (Gonal-f[®]) will be administered as routinely practiced by investigators. GnRH-a types, GnRH-a and FSH doses will be adjusted according to the clinical experiences of investigators in each site.

GnRH-ant group: Recombinant FSH (Gonal-f[®]) will be administered as routinely practiced by investigators. FSH doses will be adjusted according to the clinical experiences of investigators. The GnRH-ant (Cetrotide[®]) will be initiated in a fixed protocol on stimulation days 5 or 6 per the investigator's ART protocol.

Reference therapy:

LH supplementation: If there is slow/suboptimal response in follicular development observed by investigators, the rLH (Luveris[®]) will be administered as required. LH supplementation is based on one of the following criteria¹ :

- Having no follicle >10 mm by day 6;
- Low estradiol concentration <200 pg/ml or <732 pmol/L by day 6;

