The analyses of the secondary rate endpoints will use the same methods as the conservative CLBR and the analysis of secondary time-to-event variables will use the similar methods as the optimal CLBR, which are intended to provide additional characterization of the treatment effect.

Number of oocytes retrieved will be summarized and compared basing on analysis of variance (ANOVA) including treatment and center as factors. The treatment difference and the two-sided 95% confidence interval will be reported.

Furthermore, univariate/multivariate logistic or cox regression analysis will be performed to evaluate the dependence of Age (≤ 35 or > 35 years), AFC, AMH, number of oocytes retrieved, number of usable embryos, times of embryo transfer, and BMI in relation to pregnancy rate or CLBR.

Table X Schedule of Assessments

Procedure Visit	Screening/Baseline	Gn Initiation	Triggering Day	Oocytes pick up	Embryo Transfer		HCG Test	Clinical pregnancy assessment	Ongoing Pregnancy (fresh cycle)	Live Birth	End of Observation	2 years Follow up Visit
					fresh cycle	FET						
Demography	x											
Medical history	x											
Inclusion and exclusion criteria	x											
Signed informed consent form	x											
Physical examination and vital signs	x											
Clinical and gynecological examination	x											
FSH levels within last 3 months	x											
E ₂ level within last 3 months	x											
AMH*	x											
AFC within last 3 months	x											
Administration of GnRH-a (long protocol group)		x	x									
Administration of Gonal-f® new pen		x	x									
Administration of GnRH-ant (GnRH-ant protocol group)			x									
LH levels		x										
r-LH supplementation if need			x									
HCG trigger			x									
E ₂ level		x										
Oocytes pick up				x								

CELEBRATE Study

MS700623_0020

Procedure Visit	Screening/Baseline	Gn Initiation	Triggering Day	Oocytes pick up	Embryo Transfer		HCG Test	Clinical pregnancy assessment	Ongoing Pregnancy (fresh cycle)	Live Birth	End of Observation	2 years Follow up Visit
					fresh cycle	FET						
Embryo transfer					x	x						
Pregnancy assessment by serum β -hCG test							x					
Clinical Pregnancy assessment by ultrasound scan						x		x				
Ongoing pregnancy									x			
Live birth										x		
Safety												
OHSS			x	x								
AEs		x	x	x	x		x	x	x	x		
Concomitant medication		x	x	x	x		x	x	x	x		

* After randomization.

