7.2.1 Screening/Baseline

At the initial study visit, the subject will be informed of the study objectives and overall requirements, and written informed consent will be obtained prior to any study specific assessments. The subject will then undergo a brief clinical evaluation to ensure compliance with the inclusion and exclusion criteria to determine the eligibility (see Section 5.2).

Data for all subjects will come from the subjects' Screening or Baseline Visits and the subjects' medical records:

The following must be completed before Gn Initiation:

- Visit date
- Subject Name and hospital subject number will be recorded and kept confidentially in the clinic solely for the purposes of generating a unique study subject number which will be used to anonymously identify each subject in the study.
- Demographic details including age, gender, date of birth and ethnic origin
- Weight and height
- Clinical and gynecological examination
- Gynecological history: duration of infertility, menstrual cycle, History of miscarriages, history of pelvic surgery; history of ovarian surgery.
- Medical history and concomitant illness
- Any concomitant medication taken by the subject when entering the study
- Concomitant medications prescribed and reasons
- Ability to conceive and times of IVF attempts
- In vitro fertilization-embryo transfer and ICSI indications assessment
- The following data should be collected (data within 3 months before Screening is accepted)
 - FSH and estrogen (E2) levels during the early follicular phase (Cycle Day 2 to 4)
 - AFC (follicles ≥ 2 mm and < 11 mm) assessed in the early follicular phase (Cycle Day 2 to 4)

After randomization, blood samples for AMH test should be collected in each site, and the analysis will be performed in central lab. The analysis result of AMH test will be used in final statistical analysis, not for guiding the clinical medication.

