8.1 Sample Size

For this non-inferiority trial, a sufficient number of subjects will be enrolled to have at least 80% power to demonstrate the non-inferiority of GnRH antagonist protocol vs GnRH agonist protocol regarding the CLBR using a two-sided 95% confidence interval. The CLBR is expected to be 60% in both groups, and the non-inferiority margin is -10% (absolute). Based on these assumptions, a

sample size of 377 evaluable subjects per arm would provide 80% power to demonstrate the non-inferiority of GnRH antagonist protocol vs GnRH agonist protocol regarding the CLBR. As a result, totally about 888 subjects will be randomized, that is 444 for each treatment group after considering 15% dropout rate.

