8.5.2 Analysis of Primary Endpoints

The result of the analysis of the primary endpoint (CLBR) is essential for the non-inferiority claim. The conservative CLBR will be used to test the hypothesis in a confirmatory way.

Definition of the primary endpoint: CLBR with first live birth resulting from one initiated COS cycle.

Numerator is the No. of women got their first live birth, the Denominator is the No. of women who attempt the ovarian stimulation.

There will be two ways to calculate the CLBR:

- The conservative estimate of the cumulative live birth rate, which is based on the assumption that none of the women who do not return for a subsequent embryo transfer would have had a live birth.
- The optimal estimate of the cumulative live birth rate, which is based on the assumption that women who do not return for a subsequent embryo transfer would have had the same live birth rates as those who do return.

Conservative CLBR with the corresponding 95% confidence interval (CI) will be based on binominal distribution. The two treatments will be compared by using Chi-square test for conservative CLBR. The difference between the two treatments and its associated 95% CI based on asymptotic normal distribution will be presented. If the lower-limit of the 95% confidence interval is greater than the non-inferiority limit (-10%), the null hypothesis will be rejected and it would be claimed that GnRH antagonist protocol is non-inferior to GnRH agonist protocol regarding to the cumulative live birth rate.

Optimal CLBR will be analyzed by using Kaplan-Meier product-limit method, the rate and its 95% CI will be provided. For optimal CLBR, the two treatments will be compared using Kaplan-Meier

product-limit estimates, the difference between the two treatments and its associated 95% CI will be also presented.

Number of oocytes retrieved will be summarized and compared basing on analysis of variance (ANOVA) including treatment and center as factors. The treatment difference and the two-sided 95% confidence interval will be reported.

Furthermore, univariate/multivariate logistic or cox regression analysis will be performed to evaluate the dependence of Age (≤ 35 or > 35 years), AFC, AMH, number of oocytes retrieved, number of usable embryos, times of embryo transfer, and BMI in relation to pregnancy rate or CLBR.

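### The supplementary regressions of pregnancy and CLBR enter age only as ≤35 versus >35, although exact age is available and eligibility ends at 38; a continuous, flexible age term would use the data better

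*Combined protocol and SAP*

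**What the plan says.** Section 8.5.2 ends with an added analysis in which "univariate/multivariate logistic or cox regression analysis will be performed" for pregnancy rate or CLBR. Its purpose is to "evaluate the dependence of Age (≤ 35 or > 35 years"), followed by AFC, AMH, oocytes retrieved, usable embryos, number of transfers and BMI. The Synopsis (Statistical methods) has the same list: "evaluate the dependence of Age (≤ 35 or > 35 years), AFC, AMH, number of oocytes retrieved". Age is the only factor given a cut. No reason is given for 35, and no analysis with continuous age is described.

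Eligibility, in the Synopsis and Section 5.3.1, requires "Age ≤ 38 years old", with no lower age limit among the inclusion criteria. Section 7.2.1 collects "Demographic details including age, gender, date of birth and ethnic origin", so exact age is available.

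The confirmatory analysis is separate and unadjusted: "The two treatments will be compared by using Chi-square test for conservative CLBR", with a confidence interval for the difference. Section 8.2 mentions no stratification by age.

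**The concern.** Splitting a measured variable into two groups treats everyone within a group as alike. Here women aged 36, 37 and 38 form one level and everyone aged 35 or younger forms the other. Any change in pregnancy chance within the wide lower group is invisible to the model, and the upper group may be small.

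Two things are at stake. First, the age effect itself is estimated less precisely than the data allow. Second, if AFC, AMH or oocyte number vary with age inside the lower group, a two-level age term adjusts for age only in part, and the remainder goes into their coefficients. That matters because Section 4.3 and the exploratory endpoint (Sections 7.3.3 and 8.3.3) concern oocyte number and CLBR. This regression is the only model described that relates oocyte number to CLBR while accounting for other factors.

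**Working it through.** **1. Does age enter the main result?** Inputs from Section 8.1: "The CLBR is expected to be 60% in both groups, and the non-inferiority margin is -10% (absolute"), 80% power, and the comparison "regarding the CLBR using a two-sided 95% confidence interval".

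- n per arm = 2 × 0.60 × 0.40 × (1.960 + 0.842)² / 0.10² = 0.48 × 7.849 / 0.01 = 376.7, so 377. Power at 377 is 80.0%.
- 377 / 0.85 = 443.5, so 444 per arm and 888 in total.

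The plan's figures reproduce exactly. Age appears neither in them nor in the unadjusted comparison, so recoding age changes nothing there.

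**2. Information kept by the split if the age effect is linear.** The share kept is the squared correlation between age and the indicator for age over 35:

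R² = p(1 − p)(m₁ − m₀)² / Var(age),

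where p is the share over 35 and m₁, m₀ are the mean ages above and at or below the cut. The documents give no age distribution, so every row below is an assumption. Normal parameters are before truncation at 38.

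Two rows by hand, age in completed years:

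- Uniform 22–38: p = 3/17, m₁ = 37, m₀ = 28.5, Var = (17² − 1)/12 = 24. R² = 0.1765 × 0.8235 × 8.5² / 24 = 0.44.
- Uniform 30–38: p = 3/9, m₁ = 37, m₀ = 32.5, Var = (9² − 1)/12 = 6.667. R² = 0.2222 × 4.5² / 6.667 = 0.675.

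| Assumed ages | Women over 35, of 888 (completed years) | Kept, completed years | Kept, exact age |
|---|---|---|---|
| Normal 30, SD 4 | 49 | 22% | 27% |
| Normal 31, SD 3.5 | 59 | 25% | 32% |
| Normal 32, SD 4 | 110 | 34% | 39% |
| Normal 33, SD 3.5 | 142 | 40% | 46% |
| Uniform 22–38 | 157 | 44% | 46% |
| Uniform 25–38 | 190 | 51% | 53% |
| Uniform 30–38 | 296 | 68% | 70% |

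A younger population does worse: normal with mean 28 and SD 3.5 keeps about 7% in completed years.

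**3. If the effect is not linear.** For truncated normals with mean 28–34 and SD 3.5–4:

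- Flat to 33, then linear: the split keeps 64–79% of the age signal, a straight-line term 18–67%.
- Flat to 30, then linear: the split keeps 27–60%, a straight-line term 49–89%.

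So a straight line is not always the better coding.

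**4. Confounding left in another coefficient.** Take a covariate with correlation r to age and no effect of its own (assumed; linear approximation). The fraction of the age confounding that remains after the binary adjustment is (1 − R²) / (1 − r²R²). For r of size 0.2 to 0.4:

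- R² = 0.22: 0.78/0.991 to 0.78/0.965, or 79–81%.
- R² = 0.40: 0.60/0.984 to 0.60/0.936, or 61–64%.
- R² = 0.675: 0.325/0.973 to 0.325/0.892, or 33–36%.

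In absolute terms, assume log-odds falling by 0.05–0.08 per year and the normal 31, SD 3.5 row (SD after truncation 3.37, fraction left 0.76–0.79). The shift per SD of the covariate is 0.05 × 3.37 × 0.2 × 0.76 = 0.03 up to 0.08 × 3.37 × 0.4 × 0.79 = 0.085. The standard error is about 1/√(888 × 0.6 × 0.4) = 0.068. The shift is therefore about 0.4 to 1.2 standard errors.

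**The case against.** The strongest reply is that nothing in the trial's conclusion depends on this model. It is an add-on, and the randomised comparison is unadjusted, so age coding cannot bias it. That stands in full. The regression's place under a heading about primary endpoints might lead a reader to infer a link to the non-inferiority claim; there is none.

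A second reply is that the size of the loss is not in the documents. That also stands. A reader might infer that the split throws away most of the age information, but this needs both a fairly young population and a roughly linear effect. With uniform ages from 25 or 30 the split keeps half or more, and with a late decline it can do better than a straight line. Nor do the documents call age a main prognostic factor or say that AFC, AMH and oocyte number change with age. These are assumptions here.

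Third, a cut fixed in advance is not data-driven, and a cut at 35 within a limit of 38 is not a contradiction. Both points are correct. They answer a charge of inconsistency, but not the point that exact age is available and unused.

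Fourth, the covariate list includes oocytes, usable embryos and number of transfers, which arise after treatment starts, so their adjusted coefficients are hard to interpret however age is coded. True, and a better age term does not cure that. It only removes one avoidable weakness.

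**Conclusion.** The point holds as a minor improvement to a supplementary analysis. The documents establish that age is split at 35 in these regressions, that exact age is available, that the upper group covers about three years, and that no reason is given. The split keeps roughly 20–46% of the information on a linear age effect for truncated normals with mean 30–33 or uniform ages 22–38, and up to about 70% for ages clustered at 30–38. These figures rest on assumed age distributions and an assumed linear effect. Residual confounding in the AFC, AMH and oocyte coefficients is possible rather than shown; under the illustrative inputs it is at most a little over one standard error. The non-inferiority test, the margin and the 377/444/888 sample size are untouched.

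**What to change.** In Section 8.5.2 and the matching Synopsis sentence, state that age enters the logistic and Cox models as a continuous variable with a prespecified flexible term, for example a restricted cubic spline with few knots at stated positions. Linear age is the simpler alternative. The flexible term should be the main coding rather than an afterthought, because a straight line can do worse than the split if the decline begins late. Keep ≤35/>35 for descriptive tables only.

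The cost is a wording change, with no new data, visits or subjects. The downside is one or two extra degrees of freedom and an age effect that has to be shown as a curve or as contrasts between chosen ages rather than as one coefficient.

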8.5.3 Analysis of Secondary Endpoints

Definition of some important secondary endpoints:

Clinical pregnancy: a pregnancy diagnosed by ultra-sonographic visualization of one or more gestational sacs or definitive clinical signs of pregnancy. It includes ectopic pregnancy. Note: Multiple gestational sacs are counted as one clinical pregnancy.

Clinical pregnancy rate: the number of clinical pregnancies expressed per 100 initiated cycles, aspiration cycles, or embryo transfer cycles. Note: When clinical pregnancy rates are given, the denominator (initiated, aspirated, or embryo transfer cycles) must be specified.

Cumulative clinical pregnancy rate: Numerator is the No. of women got their first clinical pregnancy, the Denominator is the No. of women who attempt the ovarian stimulation.

Live birth rate: Numerator is the No. of women got live birth resulting from fresh cycle (multiple births considered as one live birth), the Denominator is the No. of women who attempt the ovarian stimulation.

Implantation rate: the number of gestational sacs observed divided by the number of embryos transferred.

Ongoing pregnancy: intrauterine pregnancy continued for 12 gestational weeks (detection of presence of gestational sac with fetal heartbeat by transvaginal ultrasound examination in week 12).

Time to pregnancy: time from Gn Initiation to the first clinical pregnancy.

Time to live birth: time from Gn Initiation to the first live birth.

Cancelled cycle: an ART cycle in which ovarian stimulation or monitoring has been carried out with the intention to treat, but which did not proceed to follicular aspiration or, in the case of a thawed embryo, to embryo transfer.

Miscarriage, also known as spontaneous abortion and pregnancy loss, is the natural death of an embryo or fetus before it is able to survive independently

The analysis of the secondary endpoints are intended to provide additional characterization of the treatment effect.

Number, time, percentages and related CIs will also be reported for the following secondary endpoints:

- Number of oocytes retrieved
- Good-quality embryo rate(The Istanbul Consensus1)
- hCG positive rate (in fresh cycle)
- Implantation rate (in fresh cycle)
- Clinical pregnancy rate (in fresh cycle)
- Ongoing pregnancy rate(in fresh cycle)
- Live birth rate(in fresh cycle)
- Cumulative clinical pregnancy rate
- Miscarriage rate(in fresh cycle)
- Ectopic pregnancy rate(in fresh cycle)
- Cycle cancelled rate and reason(in fresh cycle)
- Rate and severity of OHSS(in fresh cycle)
- Time to pregnancy
- Time to live birth

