Higher number of oocytes retrieved has been linked with greater chances of pregnancy (Fleming R, 1996) and will increase the efficacy and efficiency of the reproductive treatment. This is done by hyper stimulation of the ovaries by external recombinant gonadotrophins (Commenges-Ducos M, 1998. Macklon NS, 2006). Average number of follicles recruited in an ovarian stimulation cycle have risen to ten, twenty or more, which have led to the yield of enhanced number of oocytes per cycle (Edwards RG, 1996). Manipulation of menstrual physiology with the help of drugs and surgery is the key to success in ART (Matzuk M, 2008).

In clinical practice, the most common used protocols in controlled ovarian stimulation include the long protocol (GnRH-a will be used) and short protocol (GnRH-ant will be used). GnRH analogues are given to the women undergoing ovarian hyper-stimulation to obviate LH surge which may

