cause the follicles to ovulate prematurely. In order to suppress internal secretion of pituitary gonadotropin, GnRH agonists are used which help in revolutionizing the process and procedure of stimulation of the ovaries and prevention of LH (luteinizing hormone) surge. GnRH agonists utilize agonistic analogues of gonadotropins which have some amino acids substitutions in their amino acid sequence which happen to make them more competent and enhance their half lives in comparison with the natural hormones. GnRH agonists provide release of gonadotropin secretion (Copperman AB, 2013), but after 5-7d continuous application, the pituitary is no longer respond to the stimulation then become desensitization, achieve the down-regulation (JING X, 2012). So called long protocol consist of giving external gonadotropin along with GnRH agonists and causing suppression of pituitary FSH and LH. By this protocol cancellation rate is reduced and there is increase in recruitment of the follicles and getting larger number of oocytes. The incidence of premature surges of LH is also remarkably reduced. Ovarian stimulation, through the use of GnRH agonists, helps to improve pregnancy rate as a result of IVF (Macklon NS, 2006). GnRH antagonists cause sudden chemical suppression of the pituitary, thereby causing shutdown of LH (luteinizing hormone) and FSH (follicle stimulating hormone) secretion (Shrestha D, 2015). GnRH antagonists are given in the mid-cycle which prevents an early LH surge (Gordts S, 2010). No suppression occurs in the beginning of follicular phase which is an important time for recruitment of the follicles. Ovarian stimulation by GnRH antagonist protocol is not only short but also cost effective (Depalo R, 2012). Perfect synchronization of female endocrines, endometrial physiology and embryonic factors form the basis of molecular communication between the uterine endometrium and upcoming embryo which helps in implantation and subsequent conception (Cartwright JE, 2010). Changes in morphology of the endometrium and hormonal secretion ensure proper embryo transfer and implantation capable of progression to pregnancy (Gellersen B, 2014).

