6.1 Description of the Investigational Medicinal Product

This trial aims to compare GnRH antagonist or agonist **protocols** (described in section 6.2) for COS in ART treatment, not focusing on compare the efficacy and safety for **drugs** used in these two protocols. Drugs used in this study are introduced as followed.

NOTE: All the following introductions are excerpted from the full prescribing information. Dose adjustments can be performed depends on the clinical practice and the special details of each patient.

Cetrorelix acetate for injection (Cetrotide[®]) is a gonadotropin-releasing hormone (GnRH) antagonist used to prevent premature ovulation in controlled ovarian stimulation prior to assisted reproductive technologies (ART). Treatment with Cetrotide[®] should be carried out by a doctor who has experience in this type of fertility treatment. Cetrotide[®] is given by injection under the skin of the lower abdomen (belly). The recommended dose is 0.25 mg given every 24 hours, either in the morning or in the evening. Treatment starts on day 5 or 6 of ovarian stimulation, and is continued throughout the ovarian stimulation period, until the evening before or the morning of the day when the induction of ovulation (the release of eggs) is planned. Because of the risk of severe allergic reactions, the first injection should be supervised by a doctor, and the patient closely watched for 30 minutes. Further injections may be given by the patient herself, as long as she is made aware of the signs of allergic reaction and what to do if they appear. The medicine should be injected slowly at different places on the abdomen every day.

Triptorelin embonate (Diphereline[®] or Decapeptyl[®]) belongs to a group of medicines called Gonadotrophin Releasing Hormone analogues (GnRHa), often be used in ART in combination with gonadotrophins for COS in vitro fertilization and embryo transfer (IVF-ET). GnRH-a should be administered for about 14 to 20 days for down-regulation.

Follitropin alfa (Gonal-f[®]): As a r-FSH agent, Gonal-f[®] is used for COS. It is a prefilled ready to use pen device containing follitropin alfa for injection and is designed for subcutaneous self-

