6.2 Dosage and Administration

GnRH-a group: GnRH-a types, GnRH-a and FSH doses will be adjusted according to the clinical experiences of investigators in each site. GnRH-a (Diphereline[®] or Decapetyl[®]) 0.1mg administered for about 14 to 20 days for down-regulation is recommended if applicable. Gonal-f[®] will be administered as routinely practiced by investigators. (Daily dose should follow China PI)

GnRH-ant group: The GnRH-ant (Cetrotide[®]) will be initiated in a fixed protocol on stimulation days 5 or 6 per the investigator's ART protocol. Recombinant FSH (Gonal-f[®]) will be administered as routinely practiced by investigators. FSH doses will be adjusted according to the clinical experiences of investigators.

LH supplementation: If there is slow/suboptimal response in follicular development observed by investigators, the rLH (Luveris[®]) will be administered as required. LH supplementation is based on one of the following criteria:

- Having no follicle >10 mm by day 6;
- Low estradiol concentration <200 pg/ml or <732 pmol/L by day 6;
- Poor progression or slowing of follicle growth, i.e., previously 1–2 mm progression/day slowing to less than 2 mm in 3 days.

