7.2.2 Gn Initiation

After randomization, the subjects will receive either long GnRH-a protocol or GnRH- ant protocol for COS in supposed normal ovarian responders, the procedures are described as follows:

1: GnRH agonist long protocol

GnRH-a will be administered for about 14 to 20 days until down-regulation is satisfied as judged by Investigator. Satisfied down regulation criteria can be defined as: LH \leq 5 IU, E2 \leq 50 pg/ml, and **endometrium thickness \leq 6mm**. r-FSH (Gonal-f[®]) will be initiated and regimen will be as routinely practiced by Investigators and according to licensed summary of product characteristics (China) label.

The following data will be collected:

- Date of initiation of GnRH-a
- Initial Dose of GnRH-a
- Details of dose adjustments of GnRH-a if any
- LH and E2 levels before Gonal-f[®] initiation
- Date of initiation of Gonal-f[®]
- Initial dose of Gonal-f[®]
- Recording of AEs
- Concomitant medications prescribed and reasons.

2: GnRH antagonist protocol

r-FSH (Gonal-f[®]) will be initiated and regimen will be as routinely practiced by Investigators and according to licensed SmPC label.

The following data will be collected:

- LH and E2 levels before Gonal-f[®] initiation (if measured)
- Date of initiation of Gonal-f[®]
- Initial dose of Gonal-f[®]
- Recording of AEs
- Concomitant medications prescribed and reasons.
-

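### Time to pregnancy and time to live birth start at gonadotropin initiation, so the reported times leave out the agonist arm's assigned 14 to 20 days of down-regulation

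*Combined protocol and SAP*

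**What the plan says.** Section 8.5.3 gives both definitions: "Time to pregnancy: time from Gn Initiation to the first clinical pregnancy" and "Time to live birth: time from Gn Initiation to the first live birth".

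Section 7.2.2 sets the order of events. "After randomization, the subjects will receive either long GnRH-a protocol or GnRH- ant protocol for COS". In the agonist arm, "GnRH-a will be administered for about 14 to 20 days until down-regulation is satisfied as judged by Investigator", and r-FSH is started after that. In the antagonist arm r-FSH is the first drug listed, and section 6.2 adds the antagonist on stimulation day 5 or 6. Section 6.2 words the agonist duration more loosely: "administered for about 14 to 20 days for down-regulation is recommended if applicable".

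Section 6.1 says that the trial compares protocols, "not focusing on compare the efficacy and safety for" the drugs used in them. The synopsis analyses the time-to-event secondary endpoints with methods similar to those for the optimal CLBR, that is, Kaplan-Meier estimates and their between-arm difference. It also sets each woman's trial duration at two years from FSH.

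No section gives another time origin, a sensitivity analysis on the origin, or a reason for starting at Gn initiation.

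**The concern.** Gn initiation is a post-randomisation event, and the two arms reach it at different stages of their assigned treatment. The agonist arm has already completed down-regulation, which is part of the strategy it was randomised to; the antagonist arm has taken nothing. A clock started there answers how long success takes once stimulation begins. It does not answer how long success takes under the protocol a woman is assigned, which is the natural question in a comparison of protocols and for the patient counselling that section 3 gives as a purpose of the trial.

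These are the only two endpoints that measure time to success. If both arms performed identically from r-FSH onward, the reported times would show no difference, although agonist-arm women would have been on treatment for about 14 to 20 days longer.

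A smaller gap follows. A woman who stops during down-regulation has had an injection of randomised treatment and so belongs to the ITT population in 8.4. Section 8.5.1 would count her as a failure for pregnancy, but she has no Gn date and therefore no time origin.

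**Working it through.** **The plan's own figure.** The documents give no figure for the two time endpoints. The primary sample size (8.1) reproduces: (1.960 + 0.842)² × 2 × 0.60 × 0.40 / 0.10² = 7.85 × 48 ≈ 377 per arm; 377 / 0.85 = 443.5, so 444 per arm and 888 in total. No time origin enters this calculation.

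**Step 1. Order of events (6.2, 7.2.2, 8.5.3).**

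| | Agonist arm | Antagonist arm |
|---|---|---|
| Wait from randomisation to first drug | not stated | not stated |
| First protocol drug | GnRH agonist | r-FSH |
| First drug to Gn initiation | about 14-20 days | 0 days |
| Clock for both endpoints starts at | r-FSH | r-FSH |

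The omitted time from first drug is s = 14 to 20 days, in the agonist arm only.

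**Step 2. Share of time to a fresh-cycle clinical pregnancy.** From the plan: ultrasound 4 to 6 weeks (28-42 days) after transfer (7.2.8). Assumed: 10-14 stimulation days and 5-7 days from trigger to transfer.

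- Gn start to scan: 10 + 5 + 28 = 43 days, up to 14 + 7 + 42 = 63 days.
- Omitted share = s / (s + Gn-to-scan time): lowest 14 / (14 + 63) = 18.2%, highest 20 / (20 + 43) = 31.7%.

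**Step 3. Share of time to a fresh-transfer live birth.** Assumed: 2 days from trigger to retrieval, and birth at 37-41 weeks (259-287 days) counted from 14 days before retrieval.

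- Gn start to birth: 10 + 2 + (259 − 14) = 257 days, up to 14 + 2 + (287 − 14) = 289 days.
- Omitted share: 14 / (14 + 289) = 4.6%, up to 20 / (20 + 257) = 7.2%.

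**Step 4. Effect on the two-year Kaplan-Meier rate.** With the origin at first drug and a 730-day reading, the agonist arm loses only the events from its last s days. If late events are spread evenly from a starting day to day 730, the shift is points × s / (730 − starting day).

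- Pregnancies, assuming 25 points from frozen transfers over days 100-730: 25 × 14 / 630 = 0.56; 25 × 20 / 630 = 0.79 points.
- Births, assuming 15-25 points from frozen transfers over days 380-730: 15 × 14 / 350 = 0.60; 25 × 20 / 350 = 1.43 points.
- Standard error of a difference with 444 per arm: √(2 × 0.6 × 0.4 / 444) = 3.3 points at a rate of 60% (the plan's CLBR); √(2 × 0.7 × 0.3 / 444) = 3.1 points at an assumed 70%.

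The shift of roughly 0.6-1.4 points is less than half a standard error.

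**Step 5. Women without an origin.** Their number is not given in the documents, so this part cannot be sized.

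**The case against.** The strongest reply is that Gn start is a coherent clock. Follow-up runs from FSH, the primary endpoint is per initiated stimulation cycle, and its denominator is women who attempt stimulation. No stated objective concerns time under the assigned protocol, and secondary endpoints are there for additional characterisation. All of this stands. A reader might infer that the plan contradicts itself; it does not. The point concerns which question the endpoints answer.

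The reply is also right that the comparison the plan describes, a difference in Kaplan-Meier rates, hardly moves at two years. A reader might infer a large gap between the early curves. Curves drawn from first drug would indeed be 14-20 days apart in the fresh cycle. But if the arms are alike from r-FSH onward, then under the intervals of step 2 the fresh-cycle gap closes by day 77-83 (63 + 14 to 63 + 20), and no section plans a reading that early. A Kaplan-Meier median is not named for these endpoints either; medians appear only as a default descriptive statistic in 8.5.1.

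It is tempting to cite section 3, "Ovarian stimulation by GnRH antagonist protocol is not only short but also cost effective", as proof that the plan meant to measure total protocol length. That sentence concerns stimulation, which the present clock already covers. The long and short labels there are background.

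The gap for women who stop in down-regulation is narrow. The primary population is per protocol, where such women are unlikely to appear, and 8.5.1 leaves endpoint-specific missing-data rules to the SAP. No such rule for these endpoints appears in the text given.

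The reply does not remove the omission itself. One arm's assigned phase falls before the clock, in a trial that says it compares protocols, and nothing adds it back.

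**Conclusion.** The point holds for the two secondary time endpoints and should be corrected. As defined, they measure time from the start of r-FSH. Agonist-arm times omit about 14-20 days from first drug: roughly 18-32% of the time to a fresh-cycle clinical pregnancy and 5-7% of the time to a fresh-transfer birth. The days come from the plan; the percentages depend on the intervals assumed in steps 2 and 3. The duration is approximate and investigator-judged, so the omitted time will vary by woman and site.

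Two stronger readings are not supported. A reader might infer that the non-inferiority conclusion is affected: the conservative CLBR is a proportion, and neither its test nor its sample size uses this clock. A reader might also infer that the arms would differ by 14-20 days if timed from randomisation: the documents do not give the waits before the first drug, so that net difference is unknown.

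**What to change.** In 8.5.3, report both endpoints by assigned arm on these clocks:

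1. From the first protocol drug: GnRH agonist start in the agonist arm, r-FSH start in the antagonist arm. This matches the omission, and it gives an origin to women who stop during down-regulation.
2. From randomisation, for all randomised women, as the analysis that includes those who never start Gn. The ITT set in 8.4 requires at least one injection, so this analysis needs its own population statement.
3. From Gn initiation, kept as a supplementary analysis, defined as the first r-FSH dose and described as time from the start of stimulation. Naming the date matters because the Gn Initiation visit in 7.2.2 records both an agonist and a Gonal-f start date.

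The cost is SAP wording and a little more analysis. Section 7.2.2 already collects both drug start dates, and the IWRS that randomises should hold the randomisation date. There are two downsides: scheduling waits add noise to the randomisation clock, and the new curves will not share a clock with the FSH-anchored follow-up.

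Detailed censoring rules, and the conflict between the synopsis (10 months' enrolment) and 5.1 (two years' recruitment), are separate matters.
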